6. STUDY INTERVENTION(S) AND CONCOMITANT THERAPY

See [Section 10.11.8](#) for study intervention(s) and concomitant therapy for Substudy A.

6.1. Study Intervention(s) Administered

See [Section 10.11.8.1](#) for study interventions to be administered during Substudy A.

6.1.1. Administration

Standard vaccination practices must be observed and vaccine must not be injected into blood vessels. Appropriate medication and other supportive measures for management of an acute hypersensitivity reaction must be available in accordance with local guidelines for standard immunization practices.

Administration of study interventions will be performed by an unblinded appropriately qualified, trained, and vaccine-experienced member of the study staff (eg, physician, nurse, physician's assistant, nurse practitioner, pharmacist, or medical assistant) as allowed by local, state, and institutional guidance.

Study intervention administration details will be recorded on the CRF.

See [Section 10.11.8.1.1](#) (Substudy A) for study intervention administration details.

6.1.2. Medical Devices

In this study, medical devices being deployed are for the reconstitution diluent for some of the study interventions.

All medical device deficiencies (including malfunction, use error, and inadequate labeling) shall be documented and reported by the investigator throughout the clinical investigation (see [Section 8.4.9](#)) and appropriately managed by the sponsor.

6.2. Preparation, Handling, Storage, and Accountability

1. The investigator or designee must confirm that appropriate conditions (eg, temperature) have been maintained during transit for all study interventions received and any discrepancies are reported and resolved before use of the study intervention.
2. Only participants enrolled in the study may receive study intervention and only authorized site staff may supply, prepare, and/or administer study intervention.
3. All study interventions must be stored in a secure, environmentally controlled, and monitored (manual or automated recording) area in accordance with the labeled storage conditions with access limited to the investigator and authorized site staff. At a minimum, daily minimum and maximum temperatures for all site storage locations must be documented and available upon request. Data for nonworking days must indicate the minimum and maximum temperatures since previously documented upon return to business.
4. Any excursions from the study intervention label storage conditions should be reported to Pfizer upon discovery along with actions taken. The site should actively pursue options for returning the study intervention to labeled storage conditions, as soon as possible. Once an excursion is identified, the study intervention must be quarantined and not used until Pfizer provides permission to use the study intervention. Specific details regarding

the excursion definition and information to report for each excursion will be provided to the site in the IPM.

5. Any storage conditions stated in the SRSD will be superseded by the storage conditions stated on the label. See the IPM for storage conditions of the prepared study intervention.
6. Study interventions should be stored in their original containers.
7. The investigator, institution, head of the medical institution (where applicable), or authorized site staff is responsible for study intervention accountability, reconciliation, and record maintenance (ie, receipt, reconciliation, and final disposition records), such as the IPAL or sponsor-approved equivalent. All study interventions will be accounted for using a study intervention accountability form/record.
8. Further guidance and information for the final disposition of unused study interventions are provided in the IPM. All destruction must be adequately documented. If destruction is authorized to take place at the investigator site, the investigator must ensure that the materials are destroyed in compliance with applicable environmental regulations, institutional policy, and any special instructions provided by Pfizer.

Upon identification of a product complaint, notify the sponsor within 1 business day of discovery as described in the IPM.

6.2.1. Preparation and Dispensing

See the IPM for instructions on how to prepare the study intervention for administration. Study intervention should be prepared and dispensed by an unblinded appropriately qualified and experienced member of the study staff (eg, physician, nurse, physician's assistant, nurse practitioner, pharmacy assistant/technician, or pharmacist) as allowed by local, state, and institutional guidance. A second unblinded staff member will verify the dispensing.

See [Section 10.11.8.1.3.1](#) for further details regarding preparation and dispensing for Substudy A.

6.3. Assignment to Study Intervention

Allocation (randomization) of participants to vaccine groups will proceed through the use of an IRT system (IWR). The site personnel (study coordinator or specified designee) will be required to enter or select information including, but not limited to, the user's ID and password, the protocol number, and the participant number. The site personnel will then be provided with a randomization number*. The IRT system will provide a confirmation report containing the participant number, randomization number, and study intervention allocation assigned. This report will be provided to blinded or unblinded site staff as appropriate on the role/permission the user is granted and must be stored in the site's blinded or unblinded files as appropriate.

* Do not randomize until eligibility is confirmed and the participant is present.

Study intervention will be dispensed at the study visits summarized in the [SoA\(s\)](#).

6.4. Blinding

See [Section 10.11.8.2](#) for Substudy A blinding arrangements.

6.4.1. Blinding of Participants

Substudy A blinding arrangements for participants are detailed in [Section 10.11.8.2.1](#).

6.4.2. Blinding of Site Personnel

Substudy A blinding arrangements for site personnel are detailed in [Section 10.11.8.2.2](#).

6.4.3. Blinding of the Sponsor

Substudy A blinding arrangements for the sponsor are detailed in [Section 10.11.8.2.3](#).

6.4.4. Breaking the Blind

The IRT will be programmed with blind-breaking instructions. In case of an emergency, the investigator has the sole responsibility for determining if unblinding of a participant's study intervention assignment is warranted. Participant safety must always be the first consideration in making such a determination. If the investigator decides that unblinding is warranted, the investigator should make every effort to contact the study medical monitor prior to unblinding a participant's study intervention assignment unless this could delay further management of the participant. If a participant's study intervention assignment is unblinded, the sponsor must be notified within 24 hours after breaking the blind. The date and reason that the blind was broken must be recorded in the source documentation and CRF.

The study-specific IRT reference manual and IPM will provide the contact information and further details on the use of the IRT system.

6.5. Study Intervention Compliance

When participants are dosed at the site, they will receive study intervention directly from the investigator or designee, under medical supervision. The date and time of each dose administered in the clinic will be recorded in the source documents and recorded in the CRF. The dose of study intervention and study participant identification will be confirmed at the time of dosing by a member of the study site staff other than the person administering the study intervention.

6.6. Dose Modification

Dose modification is NA to this protocol.

6.7. Continued Access to Study Intervention After the End of the Study

No study intervention will be provided to participants at the end of their study participation. It is expected that participants will be treated as required with standard-of-care treatments, as advised by their usual care physician.

6.8. Treatment of Overdose

For this study, any dose of study intervention greater than 1 dose of study intervention within a 24-hour time period will be considered an overdose.

Pfizer does not recommend specific treatment for an overdose.

In the event of an overdose, the investigator should:

1. Contact the study medical monitor within 24 hours.
2. Closely monitor the participant for any AEs/SAEs and laboratory abnormalities as medically appropriate and at least until the next scheduled follow-up.
3. Document the quantity of the excess dose as well as the duration of the overdose in the CRF.
4. Overdose is reportable to Pfizer Safety **only when associated with an SAE**.

6.9. Prior and Concomitant Therapy

See [Section 10.11.8.7](#) for Substudy A prior and concomitant therapy.

7. DISCONTINUATION OF STUDY INTERVENTION AND PARTICIPANT DISCONTINUATION/WITHDRAWAL

7.1. Discontinuation of Study Intervention

Since this is a single-dose study, this section is NA.

7.2. Participant Discontinuation/Withdrawal From the Study

A participant may withdraw from the study at any time at their own request. Reasons for discontinuation from the study include the following:

- Refused further study procedures
- Lost to follow-up
- Death
- Study terminated by sponsor

- AEs
- Participant request
- Investigator request

If a participant withdraws from the study, they may request destruction of any remaining samples taken and not tested, and the investigator must document any such requests in the site study records and notify the sponsor accordingly.

If the participant withdraws from the study and also withdraws consent (see Section 7.2.1) for disclosure of future information, no further evaluations will be performed, and no additional data will be collected. The sponsor may retain and continue to use any data collected before such withdrawal of consent.

When a participant is withdrawn from the study, the investigator will complete the 6-month telephone contact if the participant has received study intervention.

7.2.1. Withdrawal of Consent

Participants who request to discontinue receipt of study intervention will remain in the study and must continue to be followed for protocol-specified follow-up procedures. The only exception to this is when a participant specifically withdraws consent for any further contact with them or persons previously authorized by the participant to provide this information. Participants should notify the investigator in writing of the decision to withdraw consent from future follow-up, whenever possible. The withdrawal of consent should be explained in detail in the medical records by the investigator, as to whether the withdrawal is only from further receipt of study intervention or also from study procedures and/or postvaccination study follow-up, and entered on the appropriate CRF page. In the event that vital status (whether the participant is alive or dead) is being measured, publicly available information should be used to determine vital status only as appropriately directed in accordance with local law.

7.3. Lost to Follow-Up

A participant will be considered lost to follow-up if the participant repeatedly fails to return for scheduled visits and is unable to be contacted by the study site.

The following actions must be taken if a participant fails to return to the clinic for a required study visit:

- The site must attempt to contact the participant and reschedule the missed visit as soon as possible. Counsel the participant on the importance of maintaining the assigned visit schedule, and ascertain whether the participant wishes to and/or should continue in the study.

- Before a participant is deemed lost to follow-up, the investigator or designee must make every effort to regain contact with the participant (where possible, 3 telephone calls and, if necessary, a certified letter to the participant's last known mailing address or local equivalent methods). These contact attempts should be documented in the participant's medical record.
- Should the participant continue to be unreachable, the participant will be considered to have withdrawn from the study.

8. STUDY ASSESSMENTS AND PROCEDURES

8.1. Administrative Procedures

The investigator (or an appropriate delegate at the investigator site) must obtain a signed and dated ICD before performing any study-specific procedures.

Study procedures and their timing are summarized in the [SoA\(s\)](#). Protocol waivers or exemptions are not allowed.

Adherence to the study design requirements, including those specified in the [SoA\(s\)](#), is essential and required for study conduct.

All screening evaluations must be completed and reviewed to confirm that potential participants meet all eligibility criteria. The investigator will maintain a screening log to record details of all participants screened and to confirm eligibility or record reasons for screening failure, as applicable.

Every effort should be made to ensure that protocol-required tests and procedures are completed as described. However, it is anticipated that from time to time there may be circumstances outside the control of the investigator that make it unfeasible to perform the test. In these cases, the investigator must take all steps necessary to ensure the safety and well-being of the participant. When a protocol-required test cannot be performed, the investigator will document the reason for the missed test and any corrective and preventive actions that they have taken to ensure that required processes are adhered to as soon as possible. The study team must be informed of these incidents in a timely manner.

For samples being collected and shipped, detailed collection, processing, storage, and shipment instructions and contact information will be provided to the investigator site prior to initiation of the study.

8.1.1. Telehealth Visits

If in-clinic study visits cannot be conducted, every effort should be made to follow up on the safety of study participants.

In the event that a clinic visit cannot be conducted, telehealth visits may be used to assess participant safety and collect data points. Telehealth includes the exchange of healthcare information and services via telecommunication technologies (eg, audio, video, videoconferencing software) remotely, allowing the participant and the investigator to communicate on aspects of clinical care, including medical advice, reminders, education, and safety monitoring.

The following assessments must be performed during a telehealth visit:

- Review and record study intervention(s), including compliance and missed doses.
- Review and record any AEs and SAEs since the last contact. Refer to [Section 10.3.3](#).
- Review and record any new concomitant medications or changes in concomitant medications since the last contact.
- Review and record contraceptive method and results of pregnancy testing. Confirm that the participant is adhering to the contraception method(s) required in the protocol. Refer to [Section 10.4](#).
- Study participants must be reminded to promptly notify site staff about any change in their health status.

Additionally, for Substudy A:

- Obtain stop dates for previously reported AEs and SAEs.
- Obtain stop dates for any reactogenicity events reported as present on the last day of e-diary completion.
- Record the use of **prohibited** medications in the CRF as noted in [Section 10.11.8.7.1](#).
- Record the use of any new nonstudy vaccines in the CRF.

8.2. Efficacy and/or Immunogenicity Assessments

See [Section 10.11.10.1](#) for Substudy A immunogenicity assessments.

8.2.1. Biological Samples

Blood samples will be used only for scientific research. Each sample will be labeled with a code so that the laboratory analyst testing the samples will not know the participant's identity, study visit, or study cohort associated with the sample. Samples that remain after performing assays outlined in the protocol may be stored by Pfizer. Unless a time limitation is required by local regulations or ethical requirements, the samples will be stored for up to 15 years after the end of the study and then destroyed. If allowed by the ICD, stored samples

may be used for additional testing to better understand the immune responses to the vaccine(s) under study in this protocol, to inform the development of other vaccines or vaccine-related products, and/or for vaccine-related assay work supporting vaccine programs. No testing of the participant's DNA will be performed.

The participant may request that their samples, if still identifiable, be destroyed at any time; however, any data already collected from those samples will still be used for this research. The biological samples may be shared with other researchers as long as confidentiality is maintained and no testing of the participant's DNA is performed.

8.3. Safety Assessments

Planned time points for all safety assessments are provided in the [SoA\(s\)](#). Unscheduled safety measurements may be obtained at any time during the study to assess any perceived safety issues.

A clinical assessment, including medical history, will be performed on all participants at their first visit to establish a baseline. Significant medical history and observations from any physical examination, if performed, will be documented in the CRF.

AEs and SAEs are collected, recorded, and reported as defined in [Section 8.4](#).

Acute reactions within the first 30 minutes after administration of the study intervention will be assessed and documented in the AE CRF.

Safety parameters also include reactogenicity e-diary reports of local reactions, systemic events (including fever), and use of antipyretic medication that occur in the 7 days after administration of the study intervention. These prospectively self-collected occurrences of local reactions and systemic events are graded as described in [Section 8.3.4](#).

8.3.1. Physical Examinations

Physical examination findings collected during the study will be considered source data and will not be required to be reported, unless otherwise noted. Any untoward physical examination findings that are identified during the active collection period and meet the definition of an AE or SAE ([Section 10.3](#)) must be reported according to the processes in [Sections 8.4.1](#) to [8.4.3](#).

For details, refer to the substudy appendix.

8.3.2. Vital Signs

Any untoward vital sign findings that are identified during the active collection period and meet the definition of an AE or SAE ([Section 10.3](#)) must be reported according to the processes in [Sections 8.4.1](#) to [8.4.3](#).

For details, refer to the substudy appendix.

8.3.3. Clinical Safety Laboratory Assessments

Clinical safety laboratory assessments will not be collected in this study. Measurement of troponin will be performed locally for potential myocarditis/pericarditis evaluation.

For details, refer to the substudy appendix.

8.3.4. Electronic Diary

All participants will be required to complete a reactogenicity e-diary after each vaccination through an application installed on a provisioned device or on the participant's own personal device. All participants will be asked to monitor and record local reactions, systemic events, and use of antipyretic medication for 7 days from the day of administration of the study intervention. The reactogenicity e-diary allows recording of these assessments only within a fixed time window, thus providing the accurate representation of the participant's experience at that time. Data on local reactions and systemic events reported in the reactogenicity e-diary will be transferred electronically to a third-party vendor, where they will be available for review by investigators and the Pfizer clinicians at all times via an internet-based portal.

At intervals agreed to by the vendor and Pfizer, these data will be transferred electronically into Pfizer's database for analysis and reporting. These data do not need to be reported by the investigator in the CRF as AEs.

Investigators (or designee) will be required to review the reactogenicity e-diary data online at frequent intervals as part of the ongoing safety review.

The investigator or designee must obtain stop dates from the participant for any ongoing local reactions, systemic events, or use of antipyretic medication on the last day that the reactogenicity e-diary was completed. The stop dates should be documented in the source documents and the information entered in the CRF.

8.3.4.1. Grading Scales

The grading scales used in this study to assess local reactions and systemic events as described below are derived from the FDA CBER guidelines on toxicity grading scales for healthy adult volunteers enrolled in preventive vaccine clinical trials.⁵⁷

8.3.4.2. Local Reactions

During the reactogenicity e-diary reporting period, participants will be asked to assess redness, swelling, and pain at the injection site and to record the symptoms in the reactogenicity e-diary. In Substudy A, local reactions will be assessed at the injection site on the right arm.

If a local reaction persists beyond the end of the reactogenicity e-diary period following vaccination, the participant will be requested to report that information. The investigator will enter this additional information in the CRF.

Participants will be provided with a measuring device. Redness and swelling will be measured and recorded in measuring device units (range: 1 to 21) and then categorized during analysis as absent, mild, moderate, or severe based on the grading scale in Table 1. Measuring device units can be converted to centimeters according to the following formula: 1 measuring device unit = 0.5 cm. Pain at the injection site will be assessed by the participant as absent, mild, moderate, or severe according to the grading scale in Table 1.

If a Grade 3 local reaction is reported in the reactogenicity e-diary, a telephone contact should occur to ascertain further details and determine whether a site visit is clinically indicated. Only an investigator or medically qualified person is able to classify a participant's local reaction as Grade 4. If a participant experiences a confirmed Grade 4 local reaction, the investigator must immediately notify the sponsor.

Table 1. Local Reaction Grading Scale

	Mild (Grade 1)	Moderate (Grade 2)	Severe (Grade 3)	Potentially Life-Threatening (Grade 4)
Pain at the injection site	Does not interfere with activity	Interferes with activity	Prevents daily activity	Emergency room visit or hospitalization for severe pain
Redness	>2.0 cm to 5.0 cm (5 to 10 measuring device units)	>5.0 cm to 10.0 cm (11 to 20 measuring device units)	>10 cm (\geq 21 measuring device units)	Necrosis or exfoliative dermatitis
Swelling	>2.0 cm to 5.0 cm (5 to 10 measuring device units)	>5.0 cm to 10.0 cm (11 to 20 measuring device units)	>10 cm (\geq 21 measuring device units)	Necrosis

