
Local and systemic reactions to the vaccine may occur.
	
The following summary represents an example QIV safety profile.
 
In adults 65 years of age and older, the most commonly reported injection-site adverse reaction was pain (41.3%). The most commonly reported systemic adverse reactions were myalgia (22.7%),
	
The study employs the use of a reactogenicity e-diary, which allows the investigator to monitor local reactions and systemic events in real time through an electronic portal. Severe reactions will require an unscheduled telephone call, and visit if required, to be conducted per protocol.

Potential Risk of Clinical Significance	Summary of Data/Rationale for Risk	Mitigation Strategy
	headache (14.4%), and malaise (13.2%). ⁶⁰	All study participants will be observed for at least 30 minutes after vaccination. AEs will be collected from signing of the ICD through 1 month and SAEs through 6 months after study vaccination.
Study Procedures		
Venipuncture will be performed during the study.	There is the risk of bleeding, bruising, hematoma formation, and infection at the venipuncture site.	Only appropriately qualified personnel will obtain the blood draw.

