10.11.2. Schema – Substudy A (Phase 1/2)

	Vaccination			1-Month Follow-Up Visit	6-Month Telephone Contact
Approximate Month (Visit Window)	0 (Day 1)			(28 to 35 Days After Vaccination)	(175 to 189 Days After Vaccination)
Visit Identifier	Visit A101			Visit A102	Visit A103
	Vaccination 1 (Right Arm)	Vaccination 2 (Left Arm)	Vaccination 3 (Right Arm)		
Group 1 (n=150)	 Combination [RSVpreF+BNT162b2]	QIV			
Group 2 (n=150)	 Combination [RSVpreF+BNT162b2]	Placebo			
Group 3 (n=150)	 Bivalent BNT162b2	Placebo			
Group 4 (n=150)	 RSVpreF	Placebo			
Group 5 (n=150)	 QIV	Placebo			
Group 6^a (n=150)	 Bivalent BNT162b2	Placebo	RSVpreF		
Group 7^a (n=150)	 Bivalent BNT162b2	QIV	RSVpreF		

a. Separate administration sites on right arm by 1 inch (2.5 cm).

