10.11.6. Substudy A Design

10.11.6.1. Overall Design

This is a Phase 1/2 randomized, parallel-group, observer-blinded substudy to describe the safety, tolerability, and immunogenicity of a combined RSVpreF and bivalent BNT162b2 (original/Omi BA.4/BA.5) vaccine [RSVpreF+BNT162b2], administered concomitantly with a seasonal influenza vaccine or administered alone. Approximately 1050 healthy participants ≥ 65 years of age will be enrolled in Substudy A.

Note: "Enrolled" means a participant's, or their legally authorized representative's, agreement to participate in a clinical study following completion of the informed consent process.

Randomization will be conducted across 2 enrollment strata (see Table 4).

Table 4. Substudy A Enrollment Strata

Enrollment Stratum	Total Number of Participants	Number of Participants per Vaccine Group	Vaccine Group Number	Vaccine Group Description
1	750	150	1	[RSVpreF+BNT162b2] administered concurrently in the opposite arm to licensed QIV
		150	2	[RSVpreF+BNT162b2] administered concurrently in the opposite arm to placebo
		150	3	Bivalent BNT162b2 administered concurrently in the opposite arm to placebo
		150	4	RSVpreF administered concurrently in the opposite arm to placebo
		150	5	Licensed QIV administered concurrently in the opposite arm to placebo
2	300	150	6	RSVpreF and bivalent BNT162b2 (2 injections in the same arm) coadministered concurrently in the opposite arm to placebo
		150	7	RSVpreF and bivalent BNT162b2 (2 injections in the same arm) coadministered concurrently in the opposite arm to QIV

All participants will be asked to complete a reactogenicity e-diary for 7 days following vaccination. Blood samples of approximately 50 mL will be collected for immunogenicity assessments prior to vaccination at Visit A101 and 1 month after vaccination (Visit A102).

E-diary data from Day 1 through Day 3 for the first 50 participants in Groups 1 to 5, and the first 20 participants in Groups 6 and 7, will be evaluated prior to enrollment of the remaining participants in each group.

AEs and SAEs will be collected from the signing of informed consent through Visit A102 (1-month follow-up visit). SAEs will be collected from the signing of informed consent through Visit A103 (6-month telephone contact).

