10.11.8.1.1. Administration

See [Section 10.11.8.1](#).

During Substudy A, all study interventions are to be administered as an intramuscular injection into the deltoid muscle of the arm, in accordance with the schema ([Section 10.11.2](#)) and the SoA ([Section 10.11.3](#)).

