2.2.1.3. Primary Safety Estimands

2.2.1.3.1. Reactogenicity Estimands

The primary estimands for the safety objective will use the treatment policy strategy and estimate the safety rate, regardless of whether an intercurrent event occurs.

Reactogenicity estimands have the following 5 attributes:

- **Treatment condition:** [RSVpreF+BNT162b2] coadministered with QIV, [RSVpreF+BNT162b2], BNT162b2, RSVpreF, QIV, RSVpreF coadministered with BNT162b2, and RSVpreF coadministered with BNT162b2 and QIV.
- **Population:** Participants as defined by the study inclusion/exclusion criteria for Substudy A.
- **Variables:** Each item included in the e-diary reported from Days 1 through 7 after vaccination (refer to [Section 3.1.2.1](#) and [Section 3.1.2.2](#)).
- **Intercurrent events:** All data collected after the intercurrent event will be included.
- **Population-level summary:** The rates of variables (each reported reactogenicity item) in each treatment condition.

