3.1.2.1.1. Presence of Local Reactions Within 7 Days After Vaccination

For the summary of the presence (yes or no) of a local reaction during the interval from Day 1 through Day 7 after vaccination, the following variables will be derived for each participant included:

- Presence (yes or no) of each local reaction on any day (Day 1 through Day 7) after vaccination.

The derivation is described in Table 2.

Table 2. Derived Variables for Each Local Reaction

Variable ^a	Yes (1)	No (0)	Missing (.)
Any day (Days 1-7) after vaccination	The participant reports the reaction as “yes” on any day (Days 1-7).	The participant reports the reaction as “no” on all 7 days or as a combination of “no” and missing on all 7 days.	The participant reports the reaction as missing on all 7 days.

a. The variable will be defined for each of the 3 local reactions.

- Presence (yes or no) of any local reaction on any day (Day 1 through Day 7) after vaccination.

For any local reaction on any day, a similar definition can be applied as given in [Table 3](#).

Table 3. Derived Variables for Any Local Reaction

Variable	Yes (1)	No (0)	Missing (.)
Any day (Days 1-7) after vaccination	The participant reports any local reaction as “yes” on any day (Days 1-7).	The participant reports all reactions as “no” on all 7 days or as a combination of “no” and missing on all 7 days for all 3 local reactions.	The participant reports all local reactions as missing on all 7 days.

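### Groups 1 and 7: reported local-reaction rates would mix prompted right-arm data with unprompted left-arm QIV reactions, because the SAP names no arm

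*Protocol*

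**What the plan says.** **Collection.** Protocol 8.3.4.2 (Local Reactions) restricts the e-diary items for redness, swelling and pain: "In Substudy A, local reactions will be assessed at the injection site on the right arm".

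**Where the vaccines go.** The schema in Protocol 10.11.2, repeated in SAP 2.3, has a right-arm column for Vaccinations 1 and 3 and a column headed "Vaccination 2 (Left Arm)" for Vaccination 2. QIV stands in the left-arm column for Groups 1 and 7 and in the right-arm column for Group 5. Table 4 of the protocol agrees. Group 1 is "RSVpreF+BNT162b2] administered concurrently in the opposite arm to licensed QIV", and Group 7 is "RSVpreF and bivalent BNT162b2 (2 injections in the same arm) coadministered concurrently in the opposite arm to QIV". Protocol 10.11.8.1.1 makes this binding by requiring injection "in accordance with the schema".

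**Analysis.** SAP 2.2.1.3.1 lists the reactogenicity conditions, beginning "RSVpreF+BNT162b2] coadministered with QIV, [RSVpreF+BNT162b2], BNT162b2, RSVpreF, QIV" and ending with the two separate-injection regimens, one of them with QIV. The summary is the rate of each e-diary item in each condition. SAP 3.1.2.1 defines the local reactions without an arm, and Table 3 scores a yes when "The participant reports any local reaction as “yes” on any day (Days 1-7)". SAP 3.1.2 also brings in AE CRF events from the 7 days after vaccination when their preferred term has been flagged, and takes the higher grade when both sources report the same event on the same day. Neither section says which arm an AE CRF event must concern.

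**The concern.** Local reactions are a primary safety endpoint. A reader of a table row labelled as the combination given with QIV, or as all three vaccines given together, will take it to describe the local tolerability of everything injected. In those two groups the QIV site is never prompted for. A QIV reaction there enters the rate only if it reaches the AE CRF under a flagged term. In Group 5 the same reaction is prompted for daily.

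The Group 1 and 7 rates therefore have no clean meaning. They start from a right-arm measurement and add an unknown share of left-arm events. Severity is affected as well: under the highest-grade rule, a left-arm AE can replace the grade of a milder right-arm e-diary entry for the same symptom.

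The QIV row of the risk table in Protocol 2.3.1 adds a further inconsistency. As mitigation for QIV reactions it says: "The study employs the use of a reactogenicity e-diary, which allows the investigator to monitor local reactions and systemic events in real time". For local reactions at the QIV site, this does not hold in Groups 1 and 7.

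**Working it through.** The plan states no figure on this point, so the check compares the texts and then illustrates the size.

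**Step 1. What is prompted, by group**

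| Group | Right arm (prompted) | Left arm (not prompted) |
|---|---|---|
| 1 | combination | QIV |
| 2 | combination | placebo |
| 3 | BNT162b2 | placebo |
| 4 | RSVpreF | placebo |
| 5 | QIV | placebo |
| 6 | BNT162b2 and RSVpreF | placebo |
| 7 | BNT162b2 and RSVpreF | QIV |

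With 150 planned per group, QIV goes to 3 × 150 = 450 participants. The QIV site is not prompted for in 2 × 150 = 300 of them.

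**Step 2. What enters the rate**

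Take a Group 1 participant with left-arm pain and no right-arm pain.
- If the pain is recorded on the AE CRF within 7 days under a flagged term, and at least one e-diary day was transmitted, SAP 3.1.2 and Table 3 score a yes.
- If it is not recorded as an AE, the score is no.

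The outcome depends on unprompted reporting. The e-diary-only sensitivity analysis in SAP 6.1.3.3 scores no in both cases. Its difference from the main analysis in Groups 1 and 7 would therefore partly reflect the arm, not missed diary days.

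**Step 3. How many participants**

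Input: injection-site pain after QIV at age 65 and over, q = 41.3%. Protocol 2.3.1 gives it as an example profile.

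- Per group: 0.413 × 150 = 61.95, about 62.
- Groups 1 and 7: 0.413 × 300 = 123.9, about 124.

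This counts participants with QIV-site pain that the e-diary does not ask about. Some would also have right-arm pain and be scored yes anyway.

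**Step 4. Gap between the right-arm rate and the either-arm rate**

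Let p be the right-arm pain rate. The documents do not give it, so p is an assumption. Under independence the gap is (1 − p)q. With no assumption about the joint distribution, it lies between max(p, q) − p and min(1, p + q) − p.

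| Assumed p | Gap, independent arms | Gap, any joint distribution |
|---|---|---|
| 20% | 0.80 × 41.3 = 33.0 points | 21.3 to 41.3 |
| 30% | 0.70 × 41.3 = 28.9 points | 11.3 to 41.3 |
| 60% | 0.40 × 41.3 = 16.5 points | 0 to 40.0 |
| 80% | 0.20 × 41.3 = 8.3 points | 0 to 20.0 |

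**Step 5. Effect of AE CRF capture**

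If a share c of the left-arm-only cases reaches the AE CRF, the reported rate is p + c × gap. Example with p = 60% and independent arms:
- c = 0: 60.0%, the right-arm rate.
- c = 0.5: 60.0 + 8.3 = 68.3%.
- c = 1: 76.5%, the either-arm rate.

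The documents fix none of p, c or the dependence between arms, so the shortfall cannot be narrowed further.

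**The case against.** The strongest reply is that the right-arm rule is deliberate and sound. The primary safety objective is to describe the combination vaccine, which always goes in the right arm. Assessing that arm makes Group 1 against Group 2, and Group 7 against Group 6, like for like at that site. The SAP variable is each e-diary item, and SAP 2.1 declares no departure from the protocol, so the restriction could be said to carry over. Reactogenicity is described group by group, and no local-reaction comparison with Group 5 is specified.

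Most of this stands, and it is why the point does not challenge the collection rule. It does not rescue the analysis. The restriction may carry over to e-diary data, but the AE CRF events pooled with them have no arm rule, and the tables would still bear the label of the full regimen.

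A reader might also infer more than the documents support:

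- *That every QIV local reaction in Groups 1 and 7 is left out, or that about 124 go unrecorded.* AEs are elicited through Visit A102 and SAP 3.1.2 pools flagged ones. These reactions are not prompted for; that does not make them unrecorded.
- *That Group 1 must resemble Group 2.* Right-arm reactions may differ when QIV is given as well, and pooled AEs can separate the groups further.
- *That severe left-arm reactions escape follow-up.* The Grade 3 telephone contact is triggered by the e-diary. However, the Visit A101 procedures ask participants to contact the site about severe injection-site reactions, with no arm limit. The QIV risk row also lists 30-minute observation and AE and SAE collection.
- *That QIV should be removed from the treatment conditions.* Participants in Groups 1 and 7 did receive it. A right-arm reaction under QIV coadministration is a valid quantity, and removing QIV would erase the difference between Groups 1 and 2.

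**Conclusion.** The point holds as a mismatch between what is measured, what is pooled and what is labelled. Followed as written, the Group 1 and 7 local-reaction rates and maximum severities are neither right-arm figures nor whole-regimen figures. They understate local reactions to the full regimen to the extent that left-arm reactions stay unreported as AEs.

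The documents do not fix that amount. The count of about 124 of 300 rests on the protocol's example QIV pain rate applying when QIV is coadministered. The point ranges above rest in addition on assumed right-arm rates, and they describe the gap before any AE CRF capture. The mismatch itself depends on none of these numbers. Systemic events are unaffected, and so are the immunogenicity objectives. The change should be made before the safety tables are produced, because it is cheap and concerns a primary endpoint.

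**What to change.** 1. In SAP 2.2.1.3.1, 3.1.2.1 and 6.1.3, leave the treatment conditions as they are. Define the variable as *local reaction at the right-arm injection site(s)* for all seven groups, and title tables and bar charts to match.
2. In SAP 3.1.2 and 3.1.2.1, add an arm rule for pooling: only AE CRF local reactions at the right arm enter this variable. This fits the stated purpose in SAP 5.3.1.1, where the AE CRF fills in missed e-diary days. Tabulate AE CRF local reactions at the left arm, or with no arm given, separately by group as unsolicited.
3. State that the Group 1 and 7 rates are not total local tolerability of the QIV-containing regimens and are not to be set against Group 5 to judge QIV-site reactions.
4. Reconcile the QIV row of the risk table in Protocol 2.3.1 with Protocol 8.3.4.2.

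**Cost.** This is SAP and protocol wording, plus one derivation rule. The documents do not say that the AE CRF records the arm, so some events may need a query. No prompted regimen-level local-reaction rate can be claimed for Groups 1 and 7.
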